# **Trial Flow**

# **Trial Schedule**

Date	Task
September 2016	Submit UNSW HREC protocol
October 2016	Submit NSW Education SERAP protocol
December 2016	School recruitment
January 2017	Confirm school involvement
February 2017	Register clinical trial protocol
February 2017	Pre-test measures
March 2017	Trial Active
June 2017	Post-test

## **Ethics**

Approved: UNSW HREC

Name: University of New South Wales Human Research Ethics

Address: [name]

Country: Australia

Submit date: 31.08.2016

Approval date:06.10.2016

Approval ID: HC16724

# **Dissemination of Results & Publication Policy**

How will research results be reported to the participants? When signing consent, participants will be asked if they would like to be emailed a 1 page summary (in the form of an infographic) of the research results upon completion of the study. This will be sent out to all participants who select this option. A summary of the results will also be published on the Black Dog Institute website.

**How will research results be reported to other academics?** The results of this study will be analysed and published in relevant academic journals. Results will also be presented at relevant academic conferences.

How will research results be reported to other stakeholders? To ensure that research results are easily understood, we will construct a one-page infographic that easily conveys the key findings of the study. This will be emailed to all stakeholders upon completion of the study. We will also offer short face-to-face presentations (where possible) to present the key findings to schools, including parent and staff presentations. A summary of the results will also be published on the Black Dog Institute website.

How will participant confidentiality be maintained? In all reports, participants will not be individually identifiable. Numerical data will be presented at the aggregate level. Any qualitative data reported will use the non-identifiable code allocated to it.

# Data Handling, Storage, Access, and Record Keeping

## **Handling, Storage and Access**

A unique identification number will be allocated to each participant. Names will only be linked to IDs for the purposes of duty of care reporting. All data files linking personal information (such as participants' names) to ID numbers will be stored separately from raw research data. Responses will be identified by the unique user ID only. All self-report data collected during the study will be stored in password protected files on secure servers at the University of New South Wales, with data files only accessible to authorised study personnel. Biological data will be labelled with participant ID only and securely stored in locations with restricted access. Smooth Sailing program complies with strict privacy and security and guidelines. Participants will create their own password-protected accounts and passwords must be supplied in order to access and submit personal data.

## **Record Keeping**

In accordance with clinical trial protocols, all data obtained in the current study will be stored securely for a minimum of 15 years.

#### **Analysis**

Data will be collected using the Black Dog Institute e-health platform. Participant data will then be exported to SPSS statistical software for analyses. Statistical analyses will be performed using SPSS 21.0 (SPSS Inc., Chicago, II, USA). The primary outcome measures will be analysed using mixed modelling which is similar to repeated-measures analysis. This type of analysis will determine any significant differences in the scores reported at time 1 (pre) and then at time 2 (post). The primary hypothesis will be evaluated by differences in pre and post scores on help-seeking questionnaires. Secondary hypotheses will be evaluated by descriptive analyses of the acceptability and feasibility questionnaires.

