- 3. Delivery of tailored program. After step allocation, Smooth Sailing delivers a program of content that is tailored to each step. Steps 0 and 1 receive online psychoeducation. Step 2 receive online psychoeducation + online self-directed Cognitive Behavioural Therapy (CBT). Steps 3 and 4 receive online psychoeducation + online self-directed CBT + additional support from the School Counsellor. Any participant who was allocated to Step 3 or 4 triggered an electronic notification alert which was automatically sent to the school counsellor for further investigation. This allowed the school counsellor to facilitate a face-to-face session within 48 hours to provide the counselling or refer on to external services. The online psychoeducation consists of five modules on i) general mental health, ii) depression, iii) anxiety, iiii) seeking help for yourself, iv) seeking help for a friend. Each of these modules contains information about definitions of mental health terms, signs and symptoms, causes of mental health problems, what to do if needing help, and strategies and tips for what a young person can do immediately. Each module is complemented by animations and illustrations to depict key messages as well as hyperlinks to other credible youth mental health services and websites including Headspace, Reachout, Kids Helpline. This content was created specifically for this service, and was reviewed by clinicians. It is designed to be self-directed, such that the youth can read and return to it whenever they wish. The online CBT module consists of a single webpage that outlines two evidence-based self-directed online cognitive behavioural therapy programs: i) MoodGym (Australian National University) and ii) Brave Online (University of Queensland). MoodGym is an interactive self-help book which helps to learn and practise skills for managing symptoms of depression and anxiety. It consists of five modules alongside questionnaires, summaries and a personal workbook. BRAVE was developed for children and teenagers who experience Separation Anxiety Disorder, Social Phobia, Specific Phobia and Generalised Anxiety Disorder. This program helps young people to learn new ways to manage their anxiety and fears. It consists of 10 sessions and is effective for reducing social worries, anxiety about separating from loved ones, fears of specific objects or situation, worries about friendships, school performance or other everyday worries. Please see Table 2 for more detail.

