#### **Pre-test/Baseline Assessment**

During the registration process, participants will complete the online battery of questionnaires including the: Demographics questionnaire; Patient Health Questionnaire (PHQ-9); Generalised Anxiety Disorder Questionnaire (GAD-7); the General Help Seeking Behaviour Questionnaire and Actual Help-seeking Behaviour Questionnaire. This will be conducted under the supervision of a researcher and teacher/school counsellor, during class time.

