# **Statistics**

Although this study is an uncontrolled acceptability trial, we will be examining differences pre and post-test. A recent systematic review of help-seeking interventions (Gulliver et al 2012) reports an effect size of d = 0.12 - 0.53 for psycho-education interventions. As such, our sample size calculations are based on using an alpha of 0.05 and effect size of 0.50. As guided by Cohen (1992), 64 participants are needed to demonstrate this effect. Given that 40% are likely to drop out, we will target 106 participants for recruitment.

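### The primary hypothesis rests on two unranked help-seeking questionnaires with no success rule, and the Actual questionnaire may also rise because alerts bring the counsellor to the student

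*Protocol*

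**What the plan says.** The Analysis section speaks of primary measures in the plural: "The primary outcome measures will be analysed using mixed modelling which is similar to repeated-measures analysis". It then adds: "The primary hypothesis will be evaluated by differences in pre and post scores on help-seeking questionnaires". The instruments listed under Pre-test/Baseline Assessment, and again at Day 43, are "the General Help Seeking Behaviour Questionnaire and Actual Help-seeking Behaviour Questionnaire". Neither is called the primary one, and no rule states whether one or both must improve. The secondary hypotheses are to be evaluated descriptively.

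The only significance level is in the Statistics section: "our sample size calculations are based on using an alpha of 0.05 and effect size of 0.50". That section concludes that "64 participants are needed to demonstrate this effect" and continues: "Given that 40% are likely to drop out, we will target 106 participants for recruitment".

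Under Intervention, item 3, allocation to Step 3 or 4 sends an automatic alert to the school counsellor. Of the alert it says: "This allowed the school counsellor to facilitate a face-to-face session within 48 hours to provide the counselling or refer on to external services". Table 1 of potential adverse events applies the same alert to any baseline score of 1 or more on PHQ-9 item 9, and the pop-up tells the student that the counsellor will make contact. The study has a single arm and no comparator.

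**The concern.** There are two separate problems.

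First, the primary outcome is not fixed. With two candidate measures, one alpha and no rule, the result could be reported as positive on whichever questionnaire moved. In an open, uncontrolled study, naming the endpoint in advance is one of the few protections available, and this is the only formal test the Protocol assigns to a stated hypothesis.

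Second, one of the two measures may respond to the trial's own procedure. The baseline questionnaires precede the alert and the post-test is at Day 43, so contact arranged after an alert falls inside the pre-post window. The stated objective is to increase help-seeking. A student approached by a counsellor after an automatic alert has received care but has not necessarily sought it, and the Analysis section does not separate the two. Without a control group, nothing subtracts this contribution.

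**Working it through.** **The plan's own figure.** Inputs from the Statistics section: alpha 0.05, d = 0.50, N = 64, 40% dropout, target 106. Power and sidedness are not stated; 80% and two-sided are assumed. A two-group comparison of means needs n = 2(1.96 + 0.84)² / 0.50² ≈ 63 per group, or 63.8, so 64, with the t distribution. Dropout: 64 / 0.6 = 106.7, against the stated 106. The figure therefore reproduces as a single test at 0.05, with no allowance for a second measure. (It is a per-group number for two groups; that is a separate matter.)

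**Two tests at 0.05, either one sufficing.** If independent, 1 − 0.95² = 0.0975. Simulated for correlated tests:

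| Correlation | Familywise error |
|---|---|
| 0 | 9.8% |
| 0.5 | 9.1% |
| 0.7 | 8.3% |
| 0.9 | 7.0% |

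If both must be significant, the error does not exceed 5%.

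**Students routed to the counsellor.** Table 2 of the Intervention section expects 10–15% at Step 3 and 5% at Step 4, together 15–20%. Among 64 completers, 0.15 × 64 = 9.6 and 0.20 × 64 = 12.8, so about 10 to 13. This assumes that dropout is unrelated to severity, and it leaves out item 9 alerts at lower steps, whose share is not stated.

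**What arranged contact alone could do to the Actual score.** Assumptions: each newly recorded contact adds one source; all other change has mean 0 and standard deviation s; 64 completers; paired t test, two-sided 0.05, 20,000 simulated trials. With alerted share q and fraction newly recorded c, the mean rise is m = qc, and the standardised change is m / √(m(1 − m) + s²). For q = 0.15, c = 1, s = 0 this is 0.15 / √0.1275 = 0.42. Share of trials significant:

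| q | c | m | s = 0 | s = 0.5 | s = 1.0 |
|---|---|---|---|---|---|
| 0.15 | 0.5 | 0.075 | 72% | 17% | 9% |
| 0.20 | 0.5 | 0.10 | 89% | 27% | 12% |
| 0.15 | 1 | 0.15 | 99% | 48% | 20% |
| 0.20 | 1 | 0.20 | over 99% | 70% | 31% |

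Every cell exceeds 5%, although no student has initiated anything new. The table holds only if such contact is recorded; if the questionnaire does not count it, or its recall period excludes it, the excess disappears.

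**A single yes/no item.** As an extreme case, suppose all 10 or all 13 alerted students switch from no to yes and nobody switches back. The exact McNemar test gives 2 × 0.5¹⁰ = 0.002 or 2 × 0.5¹³ = 0.0002. If 5 of the 10 switch, p = 2 × 0.5⁵ = 0.063. If ten switch to yes and three switch to no, p = 0.092.

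**The case against.** The case against has real weight.

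- **Inflation depends on an unstated rule.** The Protocol does not say that either questionnaire suffices, and a multiplicity rule could sit in a statistical analysis plan that is not shown. A reader might infer that the trial runs at a 10% error rate; the text supports that only conditionally. It is still true that choosing the primary outcome belongs in the protocol, and this one names two measures without choosing.
- **The instrument is unseen.** A reader might infer that the Actual questionnaire is positive by construction. The documents do not say that it counts counsellor contact, counts contact the student did not start, or covers the relevant weeks. The first session may fall within 48 hours of baseline, so a recall period much shorter than six weeks would miss it.
- **The small p-values are a worst case.** Results of 0.002 to 0.0002 need every alerted student to switch and none to switch back. The planned analysis is also a mixed model of scores, not a McNemar test on one item.
- **The contact is worded permissively and is part of the service.** The alert enables a session, and follow-up uses normal school protocols. Counsellor support is a declared component at Steps 3 and 4. That makes the contact legitimate care, but does not make it help sought by the student.
- **Study purpose.** The Statistics section calls this an acceptability trial, which lowers the stakes of a conditional 7–10% error rate.

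A tempting remedy is to discount every counsellor contact after an alert. That would also remove visits the student chose to make, and only at post-test, biasing the change downward in the most symptomatic students. The documents describe counts of alert emails, but no record of who initiated a contact.

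**Conclusion.** The first part holds on the text: two unranked questionnaires, one alpha of 0.05 and no success rule. Its size is a familywise error of about 7–10% if either measure suffices, and no inflation if both are required.

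The second part holds conditionally. The mechanism is in the Protocol: automatic alert, counsellor-initiated contact inside the 43-day window, no control group. Whether it reaches the Actual score depends on Appendix B and on the recall period. If it does, the chance of a significant rise from arranged contact alone is anywhere from about 9% to over 99% under the assumed variability and recording rates. The supportable statement is that the score can rise without student-initiated help-seeking, not that it will. The first part does not depend on the second.

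**What to change.** In the Analysis section, do one of the following:

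- Name one help-seeking questionnaire, pre to Day 43, as the single primary outcome at 0.05, and make the other key secondary. The General questionnaire is the one less exposed to arranged contact. No alpha split is then needed.
- State that both must improve, each at 0.05. With 64 pairs and a standardised paired change of 0.5, power per test is 97.6%, so joint power is at least 2 × 0.976 − 1 = 95.2%. At 0.3 it is 65.7% per test, so joint power could be as low as 2 × 0.657 − 1 = 31.4%.

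Report the Actual questionnaire for all students. Beside it, give a sensitivity analysis either restricted to students with no alert, or with the school-counsellor source removed at both pre and post. Removing it at both times keeps the comparison symmetric. State in advance that an increase confined to alerted students will not be read as increased help-seeking.

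The cost is a few sentences and one extra derivation, with no change to care or data collection. With a single primary on the General questionnaire, the behavioural measure loses co-primary status. The sensitivity result will be less precise and may be smaller: leaving out 10 to 13 of 64 leaves about 51 to 54 students, fewer once item 9 alerts are also excluded.
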